This innovative paradigm will lay the groundwork for future studies that can directly interrogate ACh function in the living human brain. This is critical to the advancement of our understanding of ACh involvement in psychiatric and medical disorders.

Additionally, a substantial literature body demonstrates that nAChRs and the cholinergic system dynamically control the mesolimbic DA system by enhancing, inhibiting, and filtering striatal DA release. We have preliminary data suggesting tobacco smokers at 2 weeks of abstinence have blunted DA release compared to nonsmokers. We propose in Aim 7 to determine 1)

whether there is reduced DA release in smokers at 2 weeks of withdrawal vs. nonsmokers, 2) if the magnitude of DA release is correlated with alterations in ACh levels measured in Aim 4 and 3) if alterations in DA and ACh predict relapse vulnerability.

**Aim 1: To determine the test-retest reproducibility of NCFHEB binding parameters in 10 nonsmoking subjects.**  $\beta_2$ -nAChRs will be quantified twice in nonsmoking subjects. Based on preclinical evidence, we hypothesize within 20% difference of binding parameters between test and retest scans.

**CLOSED Aim 2: To determine if  $\beta_2$ -nAChR availability is genetically predisposed in never smokers and smokers** We propose to determine if the ANKK1 genotype (rs4938015/hCV38879) or CHRNA4 genotype determines  $\beta_2$ -nAChR availability in adult never smokers. Specifically, 10 never smokers and 10 smokers at one week of abstinence will be imaged using NCFHEB PET and blood samples for DNA extraction will be collected from all subjects.

**Hypothesis:** Homozygotes (TT) will have higher  $\beta_2$ -nAChR availability compared to age-, and sex matched heterozygotes that carry the C allele in the ANKK1 gene (rs4938015/ hCV38879).

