**CLOSED Aim 3: To determine if the adaptive increase in  $\beta_2$ -nAChR availability and change in  $\beta_2$ -nAChR availability over the first month of abstinence in smokers is genetically predisposed.** We will determine if ANKK1 or CHRNA4 genotypes are associated with changes in  $\beta_2$ -nAChR availability in smokers over time recruited in aim 2. The same smokers from Aim 2 will be supported to maintain abstinence for 4-8 weeks. Smokers that successfully abstain for 4-8 weeks (~ 50%; e.g. 5 smokers) will be imaged a second time using NCFHEB and PET. The % change in  $\beta_2$ -nAChR availability will be determined as the difference in NCFHEB binding  $[(V_T/f_p @7\text{days of abstinence} - V_T/f_p @4\text{ wks abstinence})/V_T/f_p @7\text{ days abstinence}]$ . Blood samples for DNA extraction will be collected from all subjects.

**Hypothesis:** Based on our preliminary data we hypothesize that smokers that carry the A allele for hCV16178933/rs2273504 or the G allele for hCV15953820/rs2236196 genotype will have higher  $\beta_2$ -nAChR availability at 7-9 days of abstinence compared to never smokers matched for age and sex and genotype. Whereas smoker homozygotes (GG and AA respectively for hCV16178933/rs2273504 or for hCV15953820/rs2236196) will demonstrate similar  $\beta_2$ -nAChR availability compared to never smokers. We also hypothesize that CC homozygotes for the CHRNA4 rs2273502 will show a pronounced decrease in  $\beta_2$ -nAChR availability while carriers of the T allele show no change in  $\beta_2$ -nAChR availability will demonstrate the greatest change or normalization over 6 weeks of abstinence.

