### 3.7 Statistical analysis.

**3.7 a Power Analysis in Never Smokers:** Assuming Hardy-Weinberg equilibrium, the allele frequency predicts that 30 will be homozygous (CC); 25 will be heterozygous (CT) and 5 will be homozygous (TT) for the ANKK1 alleles, and 11 will be homozygous (AA) 29 will be heterozygous (AG) and 20 will be homozygous (GG) for the CHRNA5 alleles. In a one-way ANOVA analysis, sample sizes of 30, 25, and 5 are obtained from the three genotypes of ANKK1 whose means are to be compared. The total sample of 30 subjects achieves 0.96 power to detect differences among the means versus the alternative of equal means using an F test with a 0.05 significance level for thalamus. The size of the variation in the means is represented by their standard deviation which is 17.49. The common standard deviation within a group is assumed to be 32.30. The other powers are 0.95, 0.87, and 0.99 for ANKK1 for the brain regions of striatum, cerebellum and cortex, respectively. We have enough power to detect the effect with the proposed sample size. We aim to recruit at least 10 subjects that are homozygous for TT; if we do not achieve our goals for the rarer genotype by the end of year 3; we will screen subjects prior to imaging them in year 4.

**3.7.b Power Analysis in Smokers:** The group means of  $\alpha_2$ -nAChR availability for the heterozygotes of hCV16178933/rs2273504 or hCV15953820/rs2236196 are higher in smokers than non-smokers in the brain regions of striatum, cerebellum and mean cortex, but not thalamus. We can achieve 0.81 power to detect a difference of 11.7 in striatum between the null hypothesis that both group means are 97.5 and the alternative hypothesis that the mean of non-smoking group is 85.8 with estimated group standard deviations of 14.9 and 10.8 and with a significance level (alpha) of 0.05000 using a one-sided two-sample t-test for hCV16178933/rs2273504. The other powers are 0.97, 0.95 for hCV16178933/rs2273504 and for cerebellum and mean cortex, respectively. The differences do not present in the homozygote subjects. We can also achieve 0.98 to 0.99 for hCV15953820/rs2236196 in the brain regions of striatum, cerebellum and mean cortex.

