**Never Smokers:** In a one-way ANOVA analysis, sample sizes of 30, 25, and 5 are obtained from the three genotypes of ANKK1 whose means are to be compared. The total sample of 30 subjects achieves 0.96 power to detect differences among the means versus the alternative of equal means using an F test with a 0.05 significance level for thalamus. The size of the variation in the means

is represented by their standard deviation which is 17.49. The common standard deviation within a group is assumed to be 32.30. The other powers are 0.95, 0.87, and 0.99 for ANKK1 for the brain regions of striatum, cerebellum and cortex, respectively. We have enough power to detect the effect with the proposed sample size. We aim to recruit at least 10 subjects that are homozygous for TT; if we do not achieve our goals for the rarer genotype by the end of year 3; we will screen subjects prior to imaging them in year 4.

**Smokers:** The group means of  $b_2$ -nAChR availability for the heterozygotes of hCV16178933/rs2273504 or hCV15953820/rs2236196 are higher in smokers than non-smokers in the brain regions of striatum, cerebellum and mean cortex, but not thalamus. We can achieve 0.81 power to detect a difference of 11.7 in striatum between the null hypothesis that both group means are 97.5 and the alternative hypothesis that the mean of non-smoking group is 85.8 with estimated group standard deviations of 14.9 and 10.8 and with a significance level (alpha) of 0.05000 using a one-sided two-sample t-test for hCV16178933/rs2273504. The other powers are 0.97, 0.95 for hCV16178933/rs2273504 and for cerebellum and mean cortex, respectively. The differences do not present in the homozygote subjects. We can also achieve 0.98 to 0.99 for hCV15953820/rs2236196 in the brain regions of striatum, cerebellum and mean cortex.

Genotype quality control – genotyping error and missing genotype We will check the genotypes for the SNPs via the method of departures from Hardy-Weinberg equilibrium (HWE) developed by (157), and excluded genotyping errors as a likely cause of the disequilibrium. Genotyping errors and missing genotype/allele calls will be carefully examined. Those with genotyping errors will be assigned to be missing.

SECTION III: RESEARCH INVOLVING DRUGS, BIOLOGICS, RADIOTRACERS, PLACEBOS AND DEVICES

--

*If this section (or one of its parts, A or B) is not applicable, state N/A and delete the rest of the section.*

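### The genetic aims match on age and sex, but the only tests named for them use neither; if either factor predicts receptor availability, those tests are conservative and lose precision (minor)

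*Combined protocol and SAP*

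**What the plan says.** All references are to the NCFHEB protocol.

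- **Aim 2 hypothesis (Section II, Statement of Purpose).** TT homozygotes are "compared to age-, and sex matched heterozygotes that carry the C allele in the ANKK1 gene".
- **Aim 3 hypothesis (same section).** Smokers with given CHRNA4 alleles are "compared to never smokers matched for age and sex and genotype". Neither hypothesis says whether the matching is one to one or by group.
- **Section 3.7.a.** For never smokers: "In a one-way ANOVA analysis, sample sizes of 30, 25, and 5 are obtained from the three genotypes of ANKK1".
- **Section 3.7.b.** For smokers v non-smokers among heterozygotes: "We can achieve 0.81 power to detect a difference of 11.7 in striatum", with "estimated group standard deviations of 14.9 and 10.8" and "with a significance level (alpha) of 0.05000 using a one-sided two-sample t-test for hCV16178933/rs2273504".
- **Section 12, Statistical Considerations.** It repeats both calculations, again "using a one-sided two-sample t-test for hCV16178933/rs2273504".

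Section 3.7 is headed as statistical analysis, but for these aims it holds only power calculations and genotype quality control. No paired test, no age or sex term and no other model appears. Age and gender are collected on the demographic questionnaire (section 3.4a). Aims 2 and 3 are marked closed.

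**The concern.** Matching on a factor that predicts the outcome balances that factor between the groups, so it no longer adds chance variation to the difference in means. A t-test or ANOVA without the factor does not know this: it leaves the factor's variance in the error term. The standard error is then larger than it should be, the true false-positive rate falls below the nominal 5%, and a real difference is more likely to be missed. This applies to group matching as well as to one-to-one matching.

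What is at stake is precision in a small sample. Aim 2 images 10 smokers and 10 never smokers, and the t-test is restricted to heterozygotes among them, so 10 per group is a ceiling.

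**Working it through.** **Inputs.** From section 3.7.b: difference 11.7, SDs 14.9 and 10.8, one-sided alpha 0.05. From Aim 2: 10 per group. Assumed, because the documents give no value: the share R² of within-group variance that age and sex explain.

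**1. The plan's own figures.** Root-mean-square SD = √((14.9² + 10.8²)/2) = √169.3 = 13.01. No group size is given for the t-test, so 0.81 cannot be reproduced directly. Noncentral-t power is 0.80 at 16 per group and 0.82 at 17, so 0.81 implies about 16 to 17 per group. At 10 per group: SE = 13.01 × √(2/10) = 5.82, noncentrality = 11.7/5.82 = 2.01, df = 18, power 0.61.

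For the ANOVA, λ = 60 × (17.49/32.30)² = 17.6, which gives power 0.96 as stated, with N = 30 + 25 + 5 = 60 and no age or sex term.

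**2. Adding age and sex, 10 per group, groups balanced on both.** Adjusted SE = 13.01 × √(1 − R²) × √(2/10), with df = 20 − 4 = 16. The simulation columns fit both covariates to matched groups; their unadjusted values differ by a few points through simulation noise.

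| Assumed R² | Adjusted SE | 11.7/SE | Adjusted power, formula | Simulated power, unadjusted | Simulated power, adjusted |
|---|---|---|---|---|---|
| 0 | 5.82 | 2.01 | 0.61 | 0.63 | 0.62 |
| 0.20 | 5.20 | 2.25 | 0.69 | 0.61 | 0.68 |
| 0.30 | 4.87 | 2.40 | 0.74 | 0.64 | 0.75 |

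A simulation of group-level matching on sex alone (half of each sex, 10 per group) shows the conservatism. The unadjusted one-sided false-positive rate is 5.1%, 4.1%, 3.2% and 2.4% at R² of 0, 0.10, 0.20 and 0.30.

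**3. What the assumed shares mean.** Suppose sex alone carried the effect, with an equal split and a sex difference of Δ within-sex SDs. Then R² = (Δ²/4)/(Δ²/4 + 1). R² of 0.10, 0.20 and 0.50 need Δ of about 0.67, 1 and 2.

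**4. The cost if age and sex do not matter.** At 6 per group, SE = 13.01 × √(2/6) = 7.51 and noncentrality = 1.56. Dropping from 10 to 8 df lowers power from 0.42 to 0.41, about 1 point. At 10 per group the loss is under 1 point.

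**5. A strict paired test instead.** SD of differences = √(14.9² + 10.8² − 2r × 14.9 × 10.8), df = pairs − 1. At r = 0, power is 0.58 paired v 0.61 unpaired with 10 pairs, and 0.32 v 0.37 with 5 pairs. Pairing breaks even only at r of about 0.08 with 10 pairs and 0.17 with 5.

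**The case against.** The strongest reply is that these tests appear only inside power calculations, where ignoring helpful matching is conservative, and that the aims are closed. Both statements are true, and both lower the priority. They do not remove the point: no other test is named for these aims, so either these are the analysis or none is specified, and the repair is the same. Closure limits the repair to analysis and reporting.

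A reader might also infer stronger things that the documents do not support:

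- **That standard errors are certainly too large and the benefit of matching is lost.** This needs age or sex to predict receptor availability. The reference list includes the group's own paper on sex differences in availability in abstinent smokers, but the protocol gives no effect size. If the factors explain nothing, the unadjusted test is correct.
- **That the loss is severe, with a false-positive rate near 1.5% and power 0.65 v 0.82.** Those figures need a within-pair correlation of 0.5. With genotype fixed, age and sex would have to explain about half the variance, which nothing in the plan supports.
- **That a paired test is required.** One-to-one pairing is not stated, and step 5 shows that a paired test can cost power.
- **That genotype matching is ignored.** The t-test is run within heterozygotes, so genotype is already held fixed. Only age and sex are left out.
- **That the ANOVA ignores smoker matching.** It compares genotypes within never smokers. Only Aim 2's age and sex matching bears on it, and groups of 30, 25 and 5 cannot be matched one to one.

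Finally, the gap between the 16 to 17 per group implied by 0.81 and the 10 per group imaged matters more than adjustment does. It is a separate matter.

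**Conclusion.** The point holds conditionally. The design matches on age and sex, and the named tests use neither. If either factor predicts receptor availability, those tests are conservative. At 10 per group the gain in power from adjustment runs from nothing at R² = 0, to about 7 points at 20% (0.61 to 0.68) and about 11 points at 30% (0.64 to 0.75). These figures rest on the plan's striatum inputs, on groups balanced on age and sex, and on assumed shares of variance. Fewer than 10 heterozygotes per group would lower every power figure. The priority is minor, but adjustment is the better method at almost no cost.

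**What to change.** In sections 3.7 and 12:

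1. State whether matching was one to one or by group.
2. Name the analysis for Aims 2 and 3: a linear model of regional V_T/f_p on smoking status (within the stated genotype) or on genotype group (within never smokers), plus age and sex.
3. Add a pair effect only if controls were in fact matched one to one. Do not make a strict paired test the default.
4. Label the stated 0.81 as an unadjusted figure.

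The cost is a wording change and one or two degrees of freedom, about 1 point of power at 6 per group if age and sex turn out not to matter. A default paired test would risk about 3 points at 10 pairs and about 5 at 5 pairs. No new subjects, scans or data are needed. Because the aims are closed, the change applies to the analysis and its report, and the report should say when the model was fixed relative to seeing the data.

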### **3.8a Contingency Reinforcement for Smoking Cessation (healthy controls)**

We plan to image smokers whom have been abstinent from smoking for approximately 1 week (with and without schizophrenia), 2 weeks (controls only) and 6 weeks (controls only). Contingency management techniques have been successfully used to reduce CO levels in non-treatment seeking smokers by a number of investigators (158-160).

Subjects will set a quit date and prior to the quit date they meet with the research staff who will provide them with brief advice on quitting smoking based on AHCPR guidelines (The Smoking Cessation and Clinical Practice Guideline Panel and Staff, 1996). They will be advised about the risks and benefits of quitting smoking and told that they will be monitored daily to ensure abstinence. Subjects will be informed of payment schedules (see below) for CO levels indicating abstinence and also given information on how quit rates in the first week of smoking cessation predicted sustained abstinence. We use CO levels < 11 ppm to define abstinence from cigarettes. During the first week of abstinence we will obtain CO levels from subjects up to twice daily. In addition, we will obtain urine samples once daily to measure cotinine levels (a nicotine metabolite).

For each contingency management appointment, subjects will get \$10 if their CO levels are less than 11 ppm and urine cotinine levels are less than 100 ng/ml.

### **3.8b Contingency Reinforcement for Smoking Cessation (subjects with schizophrenia)**

Because it is more difficult for smokers with schizophrenia to quit smoking, they may choose to participate in this part of the study as an inpatient at CNRU. This was previously done in our HIC27532. Therefore, smokers with schizophrenia consenting to the study will be admitted to the CNRU, for approximately 1 week prior to PET scanning to ensure abstinence from smoking, this is Day 1 of the study. All antipsychotic medications will be continued. While we will not ask subjects to change antipsychotic medications, anticholinergics agents like cogentin, that interfere with radioligand binding will be suspended for a duration of the study with the approval of the subject's non-research clinician. Patients will not be responsible for paying the costs associated with this admission, whether the subject completes the study or discontinues early. Ratings of psychiatric symptoms and a Battery of Neuropsychological Assessments will be obtained by the research staff from screening until the SPECT scan. In addition, a research staff member will visit the subjects daily for behavioral counseling to assist with smoking cessation while inpatient. Expired air carbon monoxide (CO<10ppm) and daily dipstick-urinary cotinine levels will be monitored to confirm abstinence from smoking. However, in case CO is found >10ppm or positive urine cotinine is detected on the day of PET scan, which means that subject has smoked a cigarette, the scan may be cancelled and subject may be discharged from the study.

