**Aim 4: To measure the sensitivity of NCFHEB binding to changes in endogenous ACh levels in smoking and nonsmoking subjects.** After baseline quantification of  $\beta_2$ -nAChR availability, physostigmine will be administered as previously described (HIC#09100005837) and subjects will be scanned again with NCFHEB. We hypothesize there will be greater increase in ACh level (or greater reduction in radio tracer binding) in smoking as compared to nonsmoking subjects. These results will be correlated with changes in mood and cognition associated with physostigmine administration. Up to 50 smoking and 50 nonsmoking subjects will participate. Smokers that are able to remain abstinent will have a second set of baseline and post-physostigmine scans with NCFHEB 4-8 weeks later. This will allow us to determine whether ACh function changes over the course of abstinence.

**CLOSED Aim 5: To measure the sensitivity of NCFHEB binding to changes in endogenous ACh levels in smoking and nonsmoking subjects with schizophrenia.** After baseline quantification of  $\beta_2$ -nAChR availability, at 1 week of smoking abstinence, physostigmine will be administered as previously described (HIC#09100005837) and subjects will be scanned again with NCFHEB. We hypothesize there will be greater increase in ACh level (or greater reduction in radio tracer binding) in smoking as compared to nonsmoking subjects with schizophrenia, but the extent of this change will be different than in controls. These results will be correlated with changes in mood, negative and positive symptoms, and cognition associated with physostigmine administration. Up to 10 smoking and 10 nonsmoking subjects with schizophrenia will participate.

**Aim 6: To determine the efficacy of a bolus to infusion scan versus a bolus scan of NCFHEB with physostigmine challenge.** We will invite back never smokers and smokers who completed bolus scans in Aim 4 to complete one bolus to infusion scan with NCFHEB with physostigmine administration. Smokers will complete the scan at approximately one week of abstinence from smoking. We will compare the results from this scan to their Aim 4 bolus scans to determine which administration better suits a physostigmine challenge. Smokers who completed all 4 scans in Aim 4 will not be asked to return within the same year.

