**CLOSED** Aim 5. Baseline NCFHEB PET imaging will be conducted followed by administration of physostigmine. Preferably, this will be done on the same day. However, at times when there is not enough radiotracer or when a subject is not able to tolerate a longer scan day. Therefore, some subjects may complete the study over two separate days (preferably within 1 month apart based on the availability of PET scanning times and subject's schedule).

Aim 6. Subjects from Aim 4 may be asked to come back for another PET scan with physostigmine administration. Up to 8mCi of NCFHEB will be administered as a bolus plus constant infusion for the duration of the scan (up to 4 hours). Once equilibrium is reached (approximately two hours into the scan) glycopyrrolate and physostigmine will be administered and subjects will be scanned for approximately two more hours. A transmission scan will be acquired.

**CLOSED** Aim 7. Subjects from Aim 4 will be asked to come back for two [C]PHNO scans with amphetamine administration. Up to 10 mCi of PHNO will be administered. After the first scan, subjects will take amphetamine (0.5mg/kg) by mouth, and will be imaged again with PHNO. If technical difficulties arise the second PET scan will be scheduled as soon as possible (within 5 weeks). In that case, subjects may be asked to re-take amphetamine on the day of the rescheduled PHNO scan, approximately 3 hrs prior to the scan. Amphetamine dose will not exceed 50mg per scan. Subjects will not be allowed to drive home.

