## **8. Administration of physostigmine and glycopyrrolate to subjects with schizophrenia**

There are few studies with Physostigmine in schizophrenia patients (161, 162). It has been used primarily as a probe of cholinergic function to study schizophrenia, tardive dyskinesia and mania. Overall, it appears that physostigmine either improves or has no effects on symptoms in schizophrenia. In a more recent study with the related acetylcholine esterase inhibitor Rivastigmine, there appeared to be no benefit or worsening of either cognitive deficits or symptoms in schizophrenia patients (163, 164). In contrast to the studies with physostigmine and Rivastigmine, Rowntree et al. (165) observed that Diisopropylfluorophosphonate, a centrally active cholinesterase inhibitor, produced worsened symptoms among a 30% of schizophrenia patients studies. The increase in symptoms in contrast to a lowering of symptoms has been interpreted as a rebound phenomenon. In summary, the evidence available suggests that physostigmine will either have no effects or may improve symptoms in schizophrenia patients. If schizophrenia patients do experience any worsening of symptoms we will manage those symptoms as we usually do: with a range of supportive and pharmacological measures. Since patients with schizophrenia may already be on an anticholinergics e.g., benztropine or triphenhexydl, for the treatment of antipsychotic-induced motor side effects making them more sensitive to the peripheral anticholinergic effects of glycopyrrolate, we will withhold standing

anticholinergics for 24 hrs prior to each physostigmine test day in those patients who are taking anticholinergics. Withholding standing anticholinergics for 24 hours is likely to be well-tolerated.

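### Closed Aim 5 states two different anticholinergic interruptions for subjects with schizophrenia, describes tolerability only for the shorter, and under that shorter rule a split-day baseline scan could be on drug

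*Combined protocol and SAP*

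**What the plan says.** All references are to the NCFHEB protocol, in which Aim 5 is marked closed.

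- **Section 3.8b** (contingency reinforcement, subjects with schizophrenia) continues antipsychotics, but "anticholinergics agents like cogentin, that interfere with radioligand binding will be suspended for a duration of the study", with approval from the subject's non-research clinician. The reason given is interference with binding. Smokers are admitted "for approximately 1 week prior to PET scanning to ensure abstinence from smoking, this is Day 1 of the study".
- **Risks, item 8** (physostigmine and glycopyrrolate in schizophrenia) withholds standing "anticholinergics for 24 hrs prior to each physostigmine test day in those patients who are taking anticholinergics". The reason is different: these drugs treat antipsychotic-induced motor side effects, and patients already taking them may respond more strongly to glycopyrrolate, the text describing this as "making them more sensitive to the peripheral anticholinergic effects of glycopyrrolate". Clinician approval is not mentioned. The section then says: "Withholding standing anticholinergics for 24 hours is likely to be well-tolerated".
- **Section 3.5, PET, Aim 5** gives the scan order: "Baseline NCFHEB PET imaging will be conducted followed by administration of physostigmine. Preferably, this will be done on the same day". It also allows that "some subjects may complete the study over two separate days (preferably within 1 month apart".
- **Section II, Statement of Purpose, Aim 5** sets the size: "Up to 10 smoking and 10 nonsmoking subjects with schizophrenia will participate".

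**The concern.** Two passages set different off-drug periods for the same drug class in overlapping subjects, for different reasons and with different approval requirements. This matters in two ways.

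**Risk description.** The protocol assesses tolerability for one day only. Section 3.8b describes a longer interruption of drugs that the Risks section itself says are given for motor side effects, and no passage assesses that longer period.

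**Validity.** Aim 5 rests on the change in binding from baseline to post-physostigmine within a subject, and hypothesises that the extent of this change differs from controls. The 24-hour rule attaches only to physostigmine days. If a separate baseline day was not covered, a drug that section 3.8b says affects binding could be present at one scan and absent at the other. Controls are screened for regular psychotropic use (section 7), so the mismatch would arise on the schizophrenia side of that comparison.

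**Working it through.** The plan gives no figure to reproduce here. The check sets the passages side by side, with one short comparison of durations.

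**1. Does another passage settle the conflict?** The Aim 5 criteria in section 3.3 cover stable antipsychotic monotherapy, smoking abstinence and anxiolytics. The general criteria in section 7 cover other psychotropics and antidepressants. None sets an anticholinergic rule. The anxiolytic criterion is tied to PET scan days generally and so reaches both scans; item 8 is tied to physostigmine days only.

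**2. Time off drug, admitted smoker.**
- Risks item 8: 24 hours = 1 day before each physostigmine day.
- Section 3.8b: admission is Day 1, about 1 week before PET, so about 7 days if suspension starts at admission.
- As a cross-check on the length of the cessation period, Section VII pays $25 for the first day, rising by $25 each successful day, to a cap of $525: 25 + 50 + 75 + 100 + 125 + 150 = 525, or six days. That fits an admission of about a week.
- The tolerability statement therefore covers about 1 of about 7 days.

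**3. Number of subjects.** Section 3.8b sits under smoking cessation and its text describes admitted smokers. The direct conflict therefore concerns at most 10 subjects, and among them only those taking an anticholinergic. The documents do not give that fraction. Item 8 is not limited by smoking status, so the split-day issue in step 4 could reach any anticholinergic user among the 10 + 10 = 20.

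**4. Drug status at each scan, for a subject taking an anticholinergic.**

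| Rule applied | Scans on the same day | Scans on separate days |
|---|---|---|
| Section 3.8b, whole study | both off drug | both off drug |
| Risks item 8, 24 hours | both after the 24-hour withholding | baseline may be on drug, challenge off drug |

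Only one of the four cells gives discordant status.

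**5. Effect in that cell.** Let a be the true fractional reduction in binding from physostigmine. Suppose being on drug multiplies the baseline measure by (1 + d). The observed reduction, as a fraction of baseline, is

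1 − (1 − a)/(1 + d) = (a + d)/(1 + d),

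so the error is (a + d)/(1 + d) − a = d(1 − a)/(1 + d). It is zero only if d = 0 (or in the degenerate case a = 1), and its sign follows d. The documents say these drugs interfere with binding but give neither the size nor the direction of d, so no numerical bias can be stated. The formula also assumes that the drug effect on binding has gone by the challenge scan.

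**The case against.** The strongest reply is that the rules need not conflict. A subject suspended under section 3.8b also satisfies the 24-hour rule. Because 3.8b depends on clinician approval, item 8 could be a minimum for patients whose suspension was not approved. That reading is possible, but no passage states it. Even if it were intended, the longer period would still lack a tolerability statement and the split-day gap would remain for the patients left under item 8.

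Several limits on the concern do stand:

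- Aim 5 is closed, so rewording cannot change how these subjects were handled.
- The enrolment target is for one institution and the multi-site total is blank. A reader might picture sites following different rules; the documents support only one team whose actual practice is not recorded.
- The longer suspension was not unmonitored for admitted smokers. Section 3.8b describes daily staff visits and symptom ratings, and section 3.4.e lists a movement scale (AIMS). This is supervision, not an assessment of tolerability over the longer period.
- Same-day scanning is preferred, so the discordant cell may be rare or empty.

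A reader might also infer about five weeks off drug by adding the one-week admission to a month between scans. The documents do not support that: it assumes one unbroken suspension from admission to a later second scan, which nothing describes.

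**Conclusion.** The inconsistency is real and no passage resolves it. For admitted smokers, at most 10 subjects, the two passages mean about 7 days against 1 day off drug, and the risk text addresses only the 1 day. The 7-day figure assumes that suspension starts at admission. Whether section 3.8b extends to nonsmokers is unclear, so the stronger claim that both rules bind every anticholinergic user among the 20 Aim 5 subjects is not supported.

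The validity problem is conditional. It requires an anticholinergic user, the 24-hour rule in force, scans on separate days, and a baseline scan actually done on drug. Where all four hold, the change in binding mixes the physostigmine effect with a change in anticholinergic status. A reader might infer that Aim 5 as a whole is confounded; the documents do not show that, because same-day scanning or the section 3.8b rule gives concordant scans. The number of discordant pairs and the size and direction of any bias cannot be derived from the documents.

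**What to change.** **Text.** Reconcile section 3.8b with item 8 of the Risks section, and state whether the result applies to smokers only or to all subjects with schizophrenia. Make the tolerability statement and the clinician-approval wording match the period kept. Which period that should be is for the investigators and the ethics committee; this review does not choose.

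**Data already collected.** For each Aim 5 subject, record anticholinergic status at the baseline and at the physostigmine scan from existing medication records. Flag pairs with discordant status, and report the Aim 5 change in binding with and without them. If there are none, say so; that closes the validity question.

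**Cost.** A wording amendment, one data field per scan for up to 20 subjects, and one sensitivity analysis. No new procedures or visits are needed.
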